### **9.2.9 Change from both Baseline in the SSPRO-18 at Week 52.**

The SSPRO-18 scale and change from baseline in each of the domains and the total score of the SSPRO-18 scale will be summarized for each time-point by treatment group.

Comparisons of each dose of HZN-825 at Week 52 will be tested in the same manner as that described for the primary analysis of the primary endpoint, but based only on observed data.

Missing items will be handled as indicated in [Section 9.2.4](#)

### **9.2.10 Change from both Baseline in each scale of the UCLA SCTC GIT 2.0 and the total GIT score at Week 52.**

The UCLA SCTC GIT 2.0 captures SSc-related gastrointestinal activity and severity. This instrument is an improvement over the scleroderma gastrointestinal tract (SSC GIT 1.0) instrument because it is shorter (34 items versus 52 items) but still reliable and valid instrument that differentiates reflux symptoms from symptoms of distension/bloating, adds a scale to evaluate rectal incontinence because of its high prevalence in SSc and develops a composite score that captures overall gastrointestinal tract burden associated with SSc [Khanna et al., 2009].

The UCLA SCTC GIT 2.0 has 7 scales—reflux, distension/bloating, fecal soilage, diarrhea, social functioning, emotional well-being, and constipation; a total GIT score is also calculated to capture overall burden of SSc-associated gastrointestinal involvement. Items are scored on a 0 (no days) to 3 (5 – 7 days) scale (except questions 15 and 31 are yes/no questions, and are scored as 1/0, respectively) and do not require conversion to a 0 to 100 scale. The scores of the items composing each scale are summed and then divided by the total number of items in scale. For reflux, total item score will be divided by 8. For distension/bloating, total item score will be divided by 4. For fecal soilage, total item score will be divided by 3. For diarrhea, total item score will be divided by 2. For social functioning, total item score will be divided by 6. For emotional well-being, total item score will be divided by 9. For constipation, total item score will be divided by 4.

Missing items for UCLA SCTC GIT 2.0 scales and total score will be imputed according to the instructions for the questionnaire. If the scoring manual does not indicate how to impute missing data, then the scale with missing items and total score will be considered missing.

Each scale of the GIT and total GIT score with corresponding change from baseline will be summarized descriptively at each time-point by treatment group. Corresponding change from Week 52 summaries will also be provided. Comparisons of each dose of HZN-825 at Weeks

52 for the change from both baselines will be tested in the same manner as that described for the primary analysis of the primary endpoint in [Section 9.1](#), but based only on observed data.

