DISTENSION	9. ... feel bloated (a sensation of gas or air in the stomach)?					1/4= 0.25 2/4= 0.5 3/4= 0.75 4/4= 1.0 5/4= 1.25 6/4= 1.5 7/4= 1.75 8/4= 2.0 9/4= 2.25 10/4= 2.5 11/4= 2.75 12/4= 3.0 SCORE D/B=
	10. ... notice an increase in your belly, sometimes requiring you to open your belt, pants or shirt?					
	11. ... feel full after eating a small meal?					
	12. ... pass excessive gas or flatulence?					

SOILAGE	13. ... accidentally soil (dirty) your underwear before being able to get to a bathroom?					1/1= 1.0 2/1= 2.0 3/1= 3.0 SCORE S=
---------	--	--------------------------	--------------------------	--------------------------	--------------------------	--

DIARRHEA	In the past 1 week, how often did you	(CHECK ONE RESPONSE FOR EACH QUESTION)			
		No Days 	1-2 Days 	3-4 Days 	5-7 Days 
14.	... have loose stools (diarrhea)?				
	In the past 1 week, have you noticed your stools becoming	(CHECK ONE RESPONSE FOR EACH QUESTION)			
		Yes 	No 	1/2= 0.5 2/2= 1.0 3/2= 1.5 4/2= 2.0 SCORE D=	
	15. ... watery?				

SOCIAL FUNCTIONING	In the past 1 week, how often did the following interfere with social activities (such as visiting friends or relatives)?	(CHECK ONE RESPONSE FOR EACH QUESTION)			
		No Days 	1-2 Days 	3-4 Days 	5-7 Days 
16.	... Nausea				
17.	... Vomiting				
18.	... Stomach ache or pain				
19.	... Diarrhea				

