**REMEMBER: CONSTIPATION SCORE IS NOT INCLUDED IN CALCULATION OF TOTAL SCORE**

C=Constipation; D=Diarrhea; D/B=Distention/Bloating; EWB=Emotional well-being;  
R=Reflux; SF=Social functioning; S=Fecal soilage

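### The SAP divides the one-item UCLA GIT fecal soilage score by 3 instead of 1, which cuts that scale to a third and lowers the total GIT score whenever soilage is present

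*SAP*

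**What the plan says.** SAP Section 9.2.10 describes the instrument as having 34 items ("it is shorter (34 items versus 52 items"). It gives one general scoring rule: "The scores of the items composing each scale are summed and then divided by the total number of items in scale". It then lists a divisor for each of the seven scales: 8 for reflux, 4 for distension/bloating, 2 for diarrhea, 6 for social functioning, 9 for emotional well-being and 4 for constipation. For the remaining scale it says: "For fecal soilage, total item score will be divided by 3".

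The form in Protocol Section 17.7 has one question under soilage, number 13, which asks how often in the past week the patient did "accidentally soil (dirty) your underwear before being able to get to a bathroom". Its printed scoring key is "1/1= 1.0 2/1= 2.0 3/1= 3.0 SCORE S". The form builds the total by adding six scales, soilage among them, and dividing by 6. It adds a reminder: "CONSTIPATION SCORE IS NOT INCLUDED IN CALCULATION OF TOTAL SCORE". The SAP mentions a total GIT score but gives no formula for it.

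Each scale and the total score are named in exploratory endpoint 11 of Protocol Section 9.6.1.2, which is endpoint 10 in SAP Section 4.1.3.

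**The concern.** The soilage sentence is an explicit programming instruction, and it disagrees with the form, with the general rule in the same paragraph and with the SAP's item count. If it is coded as written, reported soilage means, SDs and changes come out at one third of their proper size. Any total computed from the SAP's scale scores gives incontinence a third of the weight the form gives it. Neither result could be compared with data scored by the form.

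Both Baselines are measured in Trial HZNP-HZN-825-301. If those scores were derived from the form and carried over, while the extension visits follow this SAP, Baseline and Week 52 would be on different scales.

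**Working it through.** **Inputs.** Item counts are taken from the form in Protocol 17.7, and divisors from SAP 9.2.10.

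| Scale | Questions on form | Items | SAP divisor | Maximum by form | Maximum by SAP |
|---|---|---|---|---|---|
| Reflux | 1–8 | 8 | 8 | 24/8 = 3.0 | 3.0 |
| Distension/bloating | 9–12 | 4 | 4 | 12/4 = 3.0 | 3.0 |
| Fecal soilage | 13 | 1 | **3** | 3/1 = 3.0 | **3/3 = 1.0** |
| Diarrhea | 14–15 | 2 | 2 | 4/2 = 2.0 | 2.0 |
| Social functioning | 16–21 | 6 | 6 | 18/6 = 3.0 | 3.0 |
| Emotional well-being | 22–30 | 9 | 9 | 27/9 = 3.0 | 3.0 |
| Constipation | 31–34 | 4 | 4 | 10/4 = 2.5 | 2.5 |

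**Check 1: item count.** The SAP gives 34. The form gives 8+4+1+2+6+9+4 = 34. The SAP divisors give 8+4+3+2+6+9+4 = 36. Six of the seven divisors match, and soilage accounts for the whole discrepancy of 2.

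**Check 2: question numbers.** The SAP names questions 15 and 31 as the two yes/no items and lists the scales in form order. With one soilage item, question 15 falls in diarrhea and question 31 opens constipation, as on the form. With three soilage items (13–15), question 15 would belong to soilage, constipation would start at 33, and the form would end at question 36. The SAP's own numbering therefore requires one item.

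**Effect on the soilage scale.** Write S for the response to question 13 (0, 1, 2 or 3). The form scores S/1 and the SAP scores S/3, a loss of 1 − 1/3 = 67%.

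**Effect on the total.** By the form, total = (reflux + distension/bloating + soilage + diarrhea + social functioning + emotional well-being)/6. Replacing S by S/3 lowers it by (S − S/3)/6 = S/9.

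| S | Soilage, form | Soilage, SAP | Shortfall in total |
|---|---|---|---|
| 0 | 0 | 0 | 0 |
| 1 | 1 | 0.33 | 0.11 |
| 2 | 2 | 0.67 | 0.22 |
| 3 | 3 | 1.00 | 0.33 |

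The maximum total by the form is (3+3+3+2+3+3)/6 = 17/6 = 2.83. By the SAP it is (3+3+1+2+3+3)/6 = 15/6 = 2.50.

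**Effect on change.** If all visits are scored by the SAP rule, change in soilage is one third of its true size. Change in the total is off by (change in S)/9. This is zero when soilage is stable and 0.33 for a shift of three categories.

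**If Baseline and extension visits are scored differently.** Suppose Baseline is scored by the form and Week 52 by the SAP. A subject stable at S = 3 would then show a soilage change of 1 − 3 = −2 and a contribution to change in the total of −2/6 = −0.33, with no real change.

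**The case against.** The contradiction itself is not in dispute. The case on the other side concerns how far it reaches.

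- **The total is not defined in the SAP.** The form's total is set out for the physician to complete, using the correct soilage key. If totals were taken from completed forms they would be right. This stands as a condition. However, the SAP specifies how to derive each scale, and a total programmed from those scores is the natural reading.
- **The endpoint is change, and a stable soilage score cancels in the total.** This is correct, and the error in change is (change in S)/9. But the SAP also summarizes score levels at each time point, where the full S/9 error would appear.
- **Dividing one scale by a constant is only a change of units.** With Baseline and follow-up scored alike, test statistics and p-values for soilage alone do not move. This also stands. The reported means, SDs, LS means and confidence limits would still be wrong, and the weight of soilage within the total is altered as well.
- **The stakes are limited.** This is one scale in one of 21 exploratory endpoints, and SAP Section 9 treats comparisons and p-values as descriptive. That bears on priority, not on correctness.
- **The administered version may differ from the appendix**, as the opening of Protocol Section 17 allows. This does not help the SAP, whose item count and question numbers describe this 34-item form.

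**Conclusion.** The concern holds. The divisor of 3 contradicts the form, the SAP's general rule and the SAP's item count, and neither document gives a reason for it. Soilage scores and changes would be 67% too small. The total would be too low by 0.11, 0.22 or 0.33 at soilage responses of 1, 2 or 3, with its ceiling at 2.50 instead of 2.83. Subjects with no soilage are unaffected.

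The figures for the total assume that it is computed from the SAP's scale scores by the form's six-scale average. The spurious change from mixed scoring assumes that the earlier trial used the form's key, which these documents do not show. The primary FVC analysis and the safety analyses are unaffected. The correction should be made, but it does not threaten the trial's main conclusions.

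**What to change.** In SAP Section 9.2.10, replace the soilage sentence with: *For fecal soilage, the single item score (0 to 3) is used (divided by 1).* Add the total: *(reflux + distension/bloating + fecal soilage + diarrhea + social functioning + emotional well-being)/6, with constipation excluded*, as on the form. Confirm that both sets of baseline scores from Trial HZNP-HZN-825-301 use the same derivation, or recompute them from item responses.

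The cost is one corrected sentence, one added formula, a line of code and a check of the baseline records before database lock. No new data are needed.

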#### **9.2.11 Change from both Baseline in Raynaud's phenomenon using the Raynaud's Assessment at Week 52.**

The Raynaud's Condition Score Diary captures frequency, duration and severity of Raynaud's phenomenon activity and has face, content, criterion, discriminant and construct validity in subjects with SSc [Merkel et al., 2003]. Subjects will be provided an electronic device to capture symptoms daily through Week 52. The Raynaud's Assessment score includes a 11-point scale ranging from 0 to 10 (0=no difficulty to 10=extreme difficulty) on which the patient rates the difficulty they had with their Raynaud's condition, the count of the Raynaud's attacks that were experienced that day, and the number of minutes the longest attack lasted.

Since this is a daily diary, for each of the 3 components of the Raynauds Assessment, an analysis value will be calculated for Week 52. The analysis value will be the average of the results collected within the 30 days prior to the attended (or mapped/windowed) study day corresponding to Week 52. The resulting analysis values will be summarized descriptively by visit week and treatment group. Baseline values will be summarized descriptively by treatment group as well. Comparisons of each dose of HZN-825 at Week 52 for the change from baseline will be tested in the same manner as that described for the primary analysis of the primary endpoint in [Section 9.1](#), but based only on observed data.

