2. On Day 1 (Baseline), subjects will receive the first dose of fipaxalparant (HZN-825) in this extension trial in the clinic. All Day 1 assessments should be performed before the first dose of trial drug is administered in the clinic.
3. Performed as part of the Week 52 Visit of HZNP-HZN-825-301; if applicable, the result will be considered a Trial Baseline value for this extension trial.
4. Except when strictly unavoidable, the same person should perform the assessment at each evaluation during the trial. The mRSS assessment should be performed by a qualified Investigator (or designee).
5. The lung HRCT scan should be performed within ±2 weeks of the Week 52/PD Visit.
6. DLCO can be assessed within ±2-weeks of the Week 28 and Week 52/PD Visits.
7. Daily electronic diaries will be completed for 4 weeks starting on Day 1, 4 weeks starting at the Week 22 Visit and 4 weeks starting at the Week 46 Visit.
8. Perform for WOCBP. Serum pregnancy test at [REDACTED] (or as needed). Urine pregnancy tests should also be done every 4 weeks after Day 1, which includes both in-clinic testing at scheduled visits prior to dosing [REDACTED] and at home (also a ±7-day window) by the subject and reported to the site [REDACTED]. A urine pregnancy test will also be done at the Safety Follow-up Visit.
9. A complete physical examination, including but not limited to cardiac, pulmonary, neurologic and skin assessments, as well as directed rheumatology assessments [REDACTED]
10. Vital signs (blood pressure, heart rate, respiratory rate, temperature) will be measured at each visit.
11. Additional electrocardiograms or echocardiograms will be conducted, if clinically indicated. A standard transthoracic echocardiogram will be conducted on Day 1. However, an echocardiogram that has been performed during HZNP-HZN-825-301 and within the 3 months prior to HZNP-HZN-825-302 Day 1 can serve as the Trial Baseline echocardiogram if the subject has been clinically stable.
12. See Section 9.5.3.8 for details.
13. ESR must be processed within 1 hour of the blood draw.

14. Autoantibodies include anti-centromere antibody, anti-RNA polymerase antibody, anti-topoisomerase 1 and anti-U1 small nuclear ribonucleoprotein.
15. PK samples will be collected at each of the following visits: Day 1 (pre-dose), Week 4 (pre-dose and 2 to 4 hours post-dose) and Weeks 16, 28 and 40 (pre-dose). Note: all pre-dose samples will be collected prior to any fipaxalparant (HZN-825) administration for the day.

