#### **9.1 Primary Efficacy Endpoint Analysis**

The primary efficacy endpoint will be the change from both Baselines (Trial Baseline and HZN-825 Baseline) in FVC% predicted at Week 52.

A mixed model for repeated measures (MMRM) will be fit to the data for descriptive purposes using observed change in FVC % predicted values from all planned post-Trial Baseline assessments (Weeks 16, 28, 40 and 52). The model will include the fixed covariates factors used for stratifying randomization (use of mycophenolate mofetil [yes/no] and presence of ILD [yes/no]) in the previous trial, the treatment received in the previous trial, treatment by Visit Week and Visit Week. The Trial Baseline value will be used as a continuous covariate. An unstructured covariance matrix will be used for the primary

analysis; if the model does not converge, other covariance matrices or descriptive statistics will be considered. The least squares mean (LS mean) difference in change from Trial Baseline to Week 52 in MMRM will be estimated from this model. For subjects with missing data at 1 or more time points, the available data will be included in the analysis. A similar process for the FVC % predicted for the change from HZN-825 Baseline will also be performed.

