## 9.2 Exploratory Efficacy Endpoint Analyses

Analysis of the exploratory efficacy endpoints will be conducted in the order they are listed below for both changes from HZN-825 Baseline and Trial Baseline to Week 52 as needed.

The analysis will follow the primary analysis of the primary efficacy endpoint. The analysis will be based only on observed data.

Exploratory endpoints will be summarized at each time point. Change from HZN-825 Baseline and Trial Baseline will be evaluated separately.

### 9.2.1 Change from both Baselines in HAQ-DI at Week 52

The key exploratory efficacy endpoint is the change from both baselines in HAQ-DI.

The HAQ-DI assesses the subject's level of functional ability and includes questions of fine movements of the upper extremity, locomotor activities of the lower extremity, and activities that involved both upper and lower extremities. There are 20 questions in 8 categories of functioning including dressing, rising, eating, walking, hygiene, reach, grip, and usual activities [Cole et al., 2006]. The subject's ability to accomplish each activity in the past week is indicated as: without any difficulty, with some difficulty, with much difficulty, and unable to do. Any devices that are usually used to complete activities and any categories for which help from another person is needed are also assessed.

In addition, the subject will be asked the following anchor (additional) questions at the time points specified in Section 2.1 of the protocol:

How did your systemic sclerosis limit your daily activities in the last week?

- 0: did not limit activity
- 1: mildly limited my activity
- 2: moderately limited my activity
- 3: severely limited my activity
- 4: very severely limited my activity

How has limitation of your daily activities changed since the start of the trial?

- +3: very much less limited
- +2: much less limited
- +1: a little less limited
- 0: no change
- -1: a little more limited
- -2: much more limited
- -3: very much more limited

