4. Except when strictly unavoidable, the same person should perform the assessment at each evaluation during the trial. The mRSS assessment should be performed by a qualified Investigator (or designee).
5. The lung HRCT scan should be performed within  $\pm 2$  weeks of the Week 52/PD Visit.
6. DLCO can be assessed within  $\pm 2$ -weeks of the Week 28 and Week 52/PD Visits.
7. Daily electronic diaries will be completed for 4 weeks starting on Day 1, 4 weeks starting at the Week 22 Visit and 4 weeks starting at the Week 46 Visit.
8. Perform for WOCBP. Serum pregnancy test at [REDACTED] (or as needed). Urine pregnancy tests should also be done every 4 weeks after Day 1, which includes both in-clinic testing at scheduled visits prior to dosing [REDACTED] and at home (also a  $\pm 7$ -day window) by the subject and reported to the site [REDACTED]. A urine pregnancy test will also be done at the Safety Follow-up Visit.
9. A complete physical examination, including but not limited to cardiac, pulmonary, neurologic and skin assessments, as well as directed rheumatology assessments [REDACTED]
10. Vital signs (blood pressure, heart rate, respiratory rate, temperature) will be measured at each visit.
11. Additional electrocardiograms or echocardiograms will be conducted, if clinically indicated. A standard transthoracic echocardiogram will be conducted on Day 1. However, an echocardiogram that has been performed during HZNP-HZN-825-301 and within the 3 months prior to HZNP-HZN-825-302 Day 1 can serve as the Trial Baseline echocardiogram if the subject has been clinically stable.
12. See Section 9.5.3.8 for details.
13. ESR must be processed within 1 hour of the blood draw.
14. Autoantibodies include anti-centromere antibody, anti-RNA polymerase antibody, anti-topoisomerase 1 and anti-U1 small nuclear ribonucleoprotein.
15. PK samples will be collected at each of the following visits: Day 1 (pre-dose), Week 4 (pre-dose and 2 to 4 hours post-dose) and Weeks 16, 28 and 40 (pre-dose). Note: all pre-dose samples will be collected prior to any HZN-825 administration for the day.
16. Blood samples will be collected for serum and plasma biomarkers prior to dosing on [REDACTED] as well as at the [REDACTED] Visit.

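### SAP 9.2.11 derives a Raynaud's diary value for Week 52 only, so the Week 22 diary block is unused, the Week 46 block is used in part, and the referenced MMRM has a single post-baseline time point

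*SAP*

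**What the plan says.** **Collection.** The schedule of assessments in Protocol 2.1 (footnote 7) sets the daily diary for "4 weeks starting on Day 1, 4 weeks starting at the Week 22 Visit and 4 weeks starting at the Week 46 Visit". Footnote 7 of the schedule in SAP Section 14 gives the same three blocks. In both schedules the Raynaud's row is marked at Day 1, Week 22 and Week 46, with no mark in the Week 52/premature-discontinuation column. The Day 1 mark carries footnote 3, under which, if applicable, "the result will be considered a Trial Baseline value for this extension trial". The text of SAP 9.2.11 describes collection differently: "Subjects will be provided an electronic device to capture symptoms daily through Week 52".

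**Derivation.** SAP 9.2.11 states that "for each of the 3 components of the Raynauds Assessment, an analysis value will be calculated for Week 52", and defines that value as the "average of the results collected within the 30 days prior to the attended (or mapped/windowed) study day corresponding to Week 52". It defines no other diary value. Baseline values are to be summarised, but no rule says how a baseline diary value is formed.

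**Analysis.** The group comparison follows SAP 9.1, whose model uses "observed change in FVC % predicted values from all planned post-Trial Baseline assessments (Weeks 16, 28, 40 and 52". SAP 9.2 adds: "Exploratory endpoints will be summarized at each time point". SAP 9.2.11 itself asks for summaries by visit week. SAP Section 7 bases analyses on observed data, with imputation only for exploratory purposes as needed.

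**The concern.** A repeated-measures model helps with dropout because a subject's earlier values inform the estimate at the final visit. SAP 9.2.11 supplies one post-baseline value, so the model it refers to becomes a single-visit covariance analysis of subjects who have that value. Someone who completes the Week 22 block and leaves before Week 46 is lost to the comparison, although relevant data are in the database. If those who leave tend to have worse Raynaud's scores at Week 22, the Week 52 mean change looks too favourable.

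Two further problems affect subjects who stay. The by-visit summaries requested in SAP 9.2 and 9.2.11 cannot be produced from one derived visit. And the look-back window does not line up with the block it is meant to average.

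The restriction looks inadvertent. Every other endpoint sent to the Section 9.1 model has at least two scheduled post-baseline visits.

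**Working it through.** The plan gives no sample size, dropout rate, SD or correlation for this endpoint, so there is no figure to reproduce. The check is a day count, followed by an illustration on stated assumptions.

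**1. Day count.** Take the Week *w* visit as Day 7*w* + 1, blocks of 28 days (footnote 7), and a window of the 30 days before the Week 52 visit (SAP 9.2.11).

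- Week 52 visit: 7 × 52 + 1 = Day 365. Window: Days 335 to 364.
- Day 1 block: Days 1 to 28. Overlap with the window: 0.
- Week 22 block: starts 7 × 22 + 1 = Day 155, ends Day 182. Overlap: 0, and still 0 at every visit date within the allowed windows.
- Week 46 block: starts 7 × 46 + 1 = Day 323, ends Day 350. Overlap: Days 335 to 350, which is 16 of 28 days. The first 12 days are discarded.

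Taking Week *w* as Day 7*w* gives the same overlaps. If the Week 46 and Week 52 visits move within their windows, the overlap runs from 2 to 28 days at ±7 days (Protocol 2.1) and from 6 to 26 days at ±5 days (SAP Section 14). The number of days averaged therefore depends on visit timing.

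The window opens at (335 − 1)/7 ≈ Week 47.7. A subject who starts the last block on time but stops the diary before then has no usable entry, even if the Week 52 visit is attended.

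**2. Time points in the model.** FVC has four post-baseline visits (Weeks 16, 28, 40 and 52). The Raynaud's diary as derived has one. With the Week 22 block added it would have two.

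**3. Precision (assumed inputs).** Let *d* be the fraction missing at the last block and ρ the correlation between the Week 22 and last-block values given baseline. If values are missing completely at random, the variance of the Week 52 mean with Week 22 in the model, relative to without, is 1 − *d*ρ². If baseline and both blocks have a common correlation *r*, then ρ = *r*/(1 + *r*).

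- *r* = 0.6, *d* = 0.15: ρ = 0.375; ratio = 1 − 0.15 × 0.141 = 0.98.
- *r* = 0.8, *d* = 0.30: ρ = 0.444; ratio = 1 − 0.30 × 0.198 = 0.94.

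A simulation (200 subjects, 3,000 runs, same ranges of *r* and *d*, dropout depending on the Week 22 value) gave ratios of 0.95 to 0.99, a reduction of about 1% to 5%.

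**4. Bias (assumed inputs).** In the same simulation the odds of leaving doubled per SD of worse score at Week 22. The Week-52-only estimate of mean change was too favourable by about 0.02 SD at 15% missing and up to about 0.05 SD at 30%. With Week 22 in the model the bias was about zero. When all groups followed the same dropout rule, the bias in the between-group difference was below 0.01 SD.

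A harsher setting (log-odds slope of 1 per SD, 10% to 30% dropout, correlation 0.5 to 0.7) gave 0.04 to 0.18 SD. It made no baseline adjustment, so it overstates what the planned model would show.

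**The case against.** **The endpoint is defined at Week 52, is exploratory, and its p-values are descriptive** (SAP Section 9). Protocol 9.6.3 asks only for summaries of exploratory endpoints. This stands and limits the importance of the point. It does not explain why the SAP sends the endpoint to a repeated-measures model and then gives that model one time point.

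**Stopping drug is not the same as leaving.** Subjects who stop drug are asked to attend through Week 52, and those who leave undergo the Week 52 assessments. This stands as a reason to expect less missing data. But the diary has no mark in the Week 52/premature-discontinuation column, and SAP 7.4 maps observations by study day, so an early exit visit would not normally count as Week 52. Detailed visit windows are in the TFL shells, which are not among the documents. The rule naming Week 52 alone is in the SAP itself.

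**The by-visit wording may show that Week 22 was meant to be included.** It may. The text is then inconsistent rather than a deliberate choice to discard data, and it still needs correcting.

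**Stronger readings that the documents do not support.**

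- A reader might infer that two of the three blocks, 56 of 84 diary days, are never used. Footnote 3 ties the Day 1 cell to Trial Baseline, if applicable, and baseline values are to be summarised, so the Day 1 block may be the baseline source. Only the Week 22 block clearly lacks a use. The difficulty with Day 1 is a different one. Entries made over four weeks after the first dose do not fit the pre-dose definition of Trial Baseline in SAP 7.3, and no derivation resolves this.
- A reader might also infer that the comparison between prior-treatment groups is materially biased. All groups take the same open-label dose, and nothing in the documents points to different dropout by group. If dropout is alike, that comparison is little affected.

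**Conclusion.** The point holds as a small, inexpensive improvement together with an internal inconsistency. The following rest on the text and the day count alone:

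- the Week 22 block has no analysis value;
- the referenced model has one post-baseline time point;
- subjects who leave before the Week 46 block contribute nothing to the change-from-baseline comparison;
- the Week 52 average nominally uses 16 of the 28 Week 46 diary days;
- collection through Week 52 contradicts the block schedule. The block counts follow that schedule, which Protocol 2.1 and SAP Section 14 share.

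The gain of roughly 1% to 5% in variance and the removal of about 0.02 to 0.05 SD of bias in mean change rest on assumed missingness of 15% to 30%, correlations of 0.6 to 0.8, and dropout driven by the Week 22 score. The documents supply none of these. No primary conclusion of the trial depends on this endpoint.

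**What to change.** Amend SAP 9.2.11 as follows.

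1. For each of the three components, derive the mean of the Week 22 block and the mean of the full Week 46 block. Use the latter as the Week 52 value in place of the 30-day look-back.
2. Summarise both values by prior-treatment group, and enter both as repeated measures in the Section 9.1 model for change from each Baseline.
3. Reconcile the statement of daily capture through Week 52 with the three-block schedule.
4. State whether the Day 1 to 28 block is the Trial Baseline source (footnote 3) or post-dose data, and do not use it as both. State how the diary value is formed for each Baseline.

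The cost is SAP wording and a short derivation, with matching changes to the table shells. No further data collection is needed.

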## 17.8 Raynaud's Assessment

### Raynaud's Assessment (daily on handheld)

Pick the number that best indicates the difficulty you had today with your Raynaud's condition:

A horizontal scale from 0 to 10 with labels 'No Difficulty' and 'Extreme Difficulty' at the ends.

How many Raynaud's attacks have you had today?

How many minutes did the longest attack last?

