### 7.3 Baseline Definition

Unless otherwise specified, Baseline is defined as the last non-missing observation prior to the first dose of trial drug at the baseline visit as specified. For observations occurring on the same date as the first dose of trial drug where time is not collected but the protocol specifies the evaluation must occur prior to administration of trial drug, the result occurring on the day of first trial drug administration will be considered as Baseline.

Two types of Baselines are defined as below:

- Trial Baseline, defined as the latest non-missing measurement prior to the first dose of HZN-825 (BID) in this HZNP-HZN-825-302 extension trial.
- HZN-825 Baseline, defined as the latest non-missing measurement prior to the first dose of trial drug (QD, BID, Placebo) in HZN-825-301.

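### SAP 9.2.11 averages the Raynaud's diary over the 30 days before Week 52, but the last scheduled diary block ends at about Week 50, and no Baseline derivation for the diary is stated

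*SAP*

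**What the plan says.** SAP 9.2.11 describes the collection as follows: "Subjects will be provided an electronic device to capture symptoms daily through Week 52". For each of the three diary components (difficulty score, number of attacks, length of the longest attack), "an analysis value will be calculated for Week 52", defined as the "average of the results collected within the 30 days prior to the attended (or mapped/windowed) study day corresponding to Week 52".

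The schedule describes something else. Footnote 7 in the SAP appendix begins "Daily electronic diaries will be completed for 4 weeks starting on Day 1" and goes on to two further blocks; the protocol's footnote 7 gives these in the same words, "4 weeks starting at the Week 22 Visit and 4 weeks starting at the Week 46 Visit". Both schedules mark the Raynaud's assessment at Day 1, Week 22 and Week 46, and neither marks it at Week 52.

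For Baseline, SAP 9.2.11 says only that values will be summarized. The general rule in SAP 7.3 is "Unless otherwise specified, Baseline is defined as the last non-missing observation prior to the first dose of trial drug". Protocol 2.1, footnote 3, takes the Day 1 Raynaud's assessment from the Week 52 visit of HZNP-HZN-825-301.

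**The concern.** The averaging rule is written for a diary that runs continuously to Week 52, and this trial does not have one. The contradiction lies inside the SAP itself, between 9.2.11 and its own appendix, so it is not a by-product of the SAP citing protocol version 2.2 while the current protocol is version 3.0.

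Two things follow if the rule is applied at the Week 52 visit. Diary days that subjects have filled in are left out. The number left out also depends on when the Week 46 and Week 52 visits happened to fall, so subjects' values rest on different numbers of days for reasons unrelated to their Raynaud's. SAP 9.2.11 sets no minimum number of days.

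The unstated Baseline matters because the diary item reads "Pick the number that best indicates the difficulty you had today": each entry describes one day. If the SAP 7.3 rule is applied entry by entry, the change score sets a single day against a mean of several days.

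**Working it through.** The documents state no count of diary days, so there is no figure to reproduce.

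**Inputs.** SAP 7.1: no study day zero, so Day 1 is the first dose. Footnote 7: the last block is 28 days from the Week 46 visit. SAP 9.2.11: 30 days before the Week 52 study day. Visit windows at Weeks 46 and 52: ±7 days (protocol 2.1) or ±5 days (SAP appendix).

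**Nominal timing, anchor at the Week 52 visit or target day**
- Week 46 = Day 1 + 46×7 = Day 323; block = Days 323–350.
- Week 52 = Day 1 + 52×7 = Day 365; look-back = Days 335–364.
- Overlap = Days 335–350 = 16 of 28 days (57%).
- Collected but unused: Days 323–334 = 12. Look-back days with no scheduled diary: Days 351–364 = 14.

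Counting the Week 52 day itself inside the window gives 15 instead of 16.

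**Visit timing.** With the Week 46 visit shifted by a days and the Week 52 visit by b days, overlap = min(28, 16 + a − b).
- ±7: from 16 − 14 = 2 to 28. If all 225 offset pairs are equally likely, the mean is about 16 and the central 80% about 8 to 24.
- ±5: from 16 − 10 = 6 to 16 + 10 = 26.
- Week 52 fixed at Day 365, only Week 46 moving: 9 to 23 (±7) or 11 to 21 (±5).

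**Alternative anchor.** If the last diary day (Day 350) were the day mapped to Week 52, the look-back would be Days 320–349 and would take in 27 of 28 days.

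**Precision.** Let f(n, r) be the variance of the mean of n consecutive days with unit daily variance and AR(1) correlation r: f = (1/n)[1 + 2Σ(1 − k/n)r^k], k = 1 to n − 1. The documents give no correlation, so r = 0 to 0.8 is an assumption.

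| r | f(16) | f(28) | f(16)/f(28) | 1/f(16) |
|---|---|---|---|---|
| 0 | 0.063 | 0.036 | 1.75 | 16 |
| 0.5 | 0.172 | 0.102 | 1.68 | 5.8 |
| 0.8 | 0.411 | 0.271 | 1.52 | 2.4 |

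Between-subject variance B adds to the daily within-subject variance W and dilutes this. The variance ratio for an unadjusted comparison of the Week 52 value is (B/W + f(16)) / (B/W + f(28)), with B/W also assumed:

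| B/W | r = 0 | r = 0.5 | r = 0.8 |
|---|---|---|---|
| 0.25 | 1.094 | 1.198 | 1.269 |
| 1 | 1.026 | 1.063 | 1.110 |
| 4 | 1.007 | 1.017 | 1.033 |

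The square roots run from 1.003 to 1.127, or about 0.3% to 13% on the standard error. Missed entries are not counted.

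**Baseline.** The last column of the first table is the within-subject error variance of one diary day relative to a 16-day mean: 16, 5.8 or 2.4 times.

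**Day 1 block as Baseline.** Protocol 2.1, footnote 2, says "All Day 1 assessments should be performed before the first dose of trial drug is administered in the clinic", and SAP 7.3 lets a same-day untimed result count as pre-dose. At most the Day 1 entry qualifies; the other 27 days follow dosing.

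**The case against.** **The anchor is not settled.** The SAP allows an attended or a mapped study day, the schedule has no Raynaud's mark at Week 52, and SAP 7.4 leaves window limits to the TFL shells, which are not in these documents. A reader might infer that the plan necessarily discards 12 of 28 days. The documents do not support that: if the shells map the last diary day to Week 52, 27 of 28 days are used. This stands as a condition on the count. It does not remove the point, because the SAP does not say so, the Week 52 visit is the natural reading, and the false premise of continuous capture is in 9.2.11 itself.

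**The Baseline may not be a single day.** A reader might infer that the plan sets Baseline to one diary day. That follows only if SAP 7.3 is applied entry by entry. Trial Baseline comes from a visit in HZNP-HZN-825-301 and HZN-825 Baseline lies wholly in that trial, and these documents do not show whether it supplies an averaged diary value. What stands is that 9.2.11 does not state the derivation.

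**The size is modest.** The 2 and 28 day extremes need both visits at opposite window limits. The standard-error range is for an unadjusted Week 52 value, whereas 9.2.11 uses the SAP 9.1 model with Baseline as a covariate, so it should not be read as the effect on the planned comparison. Adjustment would not necessarily make it smaller. The endpoint is one of 21 exploratory ones, and SAP 9 treats group comparisons as descriptive.

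**Conclusion.** The point holds, at minor severity. SAP 9.2.11 rests on a diary schedule that the trial does not have. With the Week 52 visit as anchor at nominal timing, 16 of 28 collected days enter the average, and the number varies between subjects with visit timing. The loss is about 0.3% to 13% on the standard error of an unadjusted Week 52 comparison, assuming AR(1) correlation 0 to 0.8 and B/W 0.25 to 4.

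A reader might go further and infer bias between groups. Nothing in the documents shows it: visit timing is not tied to Raynaud's severity or to the previous treatment group, so the cost is precision and evenness. No formal conclusion depends on this endpoint.

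The Baseline part is a gap in specification. A mismatch between one day and a multi-day mean is possible, at 2.4 to 16 times the within-subject error variance of a 16-day mean, but it is not established.

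**What to change.** In SAP 9.2.11:

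- Remove the statement that symptoms are captured every day up to Week 52.
- Define the end-of-treatment value as the mean of all entries in the 4-week block that starts at the Week 46 visit. Fix a minimum number of days before database lock, and label the value as covering about Weeks 46 to 50. At nominal timing neither rule has scheduled diary data after about Week 50, so nothing later is given up.
- State that each Baseline is the mean of pre-dose HZNP-HZN-825-301 diary entries over a comparable period, if such data exist. Otherwise use the SAP 7.3 default and report the mismatch as a limitation.
- Do not use the Day 1–28 block mean as Trial Baseline.

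The cost is SAP wording, plus one check of what diary data HZNP-HZN-825-301 holds. The diary schedule and the data already collected do not change.
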